Patients will undergo safety assessments at baseline, 2 weeks, 4 weeks, 12 weeks and every 12 weeks until treatment is completed or discontinued. All study patients must have a 28 day follow up visit after treatment is stopped.

Patients will undergo regular radiological assessments for disease recurrence at 12 weeks, 24 weeks and then every 24 weeks until 5 years (264 weeks), then yearly thereafter. DFS shall be measured from the day of randomisation until date of recurrence or death (by any cause) in the absence of recurrence by investigational site assessment.

Patients who discontinue treatment prior to disease recurrence will continue to be followed for DFS according to study plan. Following disease recurrence, patients will undergo radiological imaging for subsequent progression in accordance with local clinical practice, and will be followed for survival every 6 months until 5 years (264 weeks), post-randomisation, then yearly thereafter. Follow up will continue until the study is closed.

At disease recurrence, patients will be restaged and all sites of NSCLC relapse will be recorded. Treatments received by the patient after relapse will be determined by the physician. Post recurrence cancer treatments and procedures will be recorded. Tumour and blood sampling for biomarker, translational science and pharmacokinetics will also be performed.

Patients will be initially followed as per the study protocol until data cut-off for the primary analysis, estimated as 68-70 months following first subject randomised, based on a 28 month recruitment period. Results from the primary analysis will be reported in the Clinical Study Report. If there are meaningfully less than 70 DFS events in the IB population at the time of the primary analysis, further follow up of patients according to the same study plan may be performed until completion of the final exploratory DFS analysis (hereafter referred to as the 'final DFS analysis').

Following the primary analysis (or 'final DFS analysis' if required) patients will be followed-up for survival according to a reduced study plan (OS period) until the data cut-off for the final OS analysis. The final OS analysis will be conducted when approximately 94 OS events in the stage II-IIIA population have been observed.

Following the final OS analysis, the ADAURA study database was planned to be closed, and the collection of survival, cancer therapy, and safety data for globally recruited patients no

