Timing (timing of each visit to be calculated based on date of randomisation visit)		Day -28 to Day -1	Day 1	Week 2	Week 4	Week 12 then every 12 weeks until 3 years (156 weeks)			Week 12, Week 24 and then every 24 weeks until 5 years (264 weeks) / yearly thereafter	Every 24 weeks until 5 years (264 weeks) / yearly thereafter	
Visit window	N/A	N/A	N/A	+/- 1 day	+/- 3 days	+/-7 days		+ 7 days	+/-7 days	+/-7 days	
ECG ⁱ		X	X ^h		X	X	X				5.2.3
Echocardiogram/MUGA (for LVEF)		X				X	X				5.2.4
MRI/contrast CT of brain		X ^j									
CT of Chest and abdomen (including liver and adrenal glands) with contrast for disease control ^k		X ^l				At Week 12, Week 24 and then every 24 weeks relative to randomisation (± 7 days) until 5 years, then yearly until disease recurrence/primary analysis/‘final DFS analysis’					5.1
Other imaging ^m		X	As clinically indicated								5.1
Genetic consent and blood sample (optional) ⁿ		X									5.6

	Screening		Treatment Period					Post-Treatment			
Visit	Part I	Part II ^a	Randomisation	Week 2	Week 4	On treatment	Treatment discontinuation ^b	28 day Follow up ^c	Follow-up until disease recurrence ^d	Follow up for survival	Protocol Section
Timing (timing of each visit to be calculated based on date of randomisation visit)		Day -28 to Day -1	Day 1	Week 2	Week 4	Week 12 then every 12 weeks until 3 years (156 weeks)			Week 12, Week 24 and then every 24 weeks until 5 years (264 weeks) / yearly thereafter	Every 24 weeks until 5 years (264 weeks) / yearly thereafter	
Visit window	N/A	N/A	N/A	+/- 1 day	+/- 3 days	+/-7 days		+ 7 days	+/-7 days	+/-7 days	
Plasma sample for ctDNA and blood borne biomarkers ^e			X (pre dose)			X	X		X		5.7.3
PK blood sample (AZD9291 and metabolites)					X ^p	X ^p					5.4
SF – 36			X (pre dose)			X ^q	X				5.3.4.1
Health Resource Module ^r			X (pre dose)	X	X	X	X				5.3.4.4
Adverse event review					X			X ^s			6
Treatment dispensed/returned			X		X	X					7.7
Concomitant medication					X						7.8

	Screening		Treatment Period					Post-Treatment			
Visit	Part I	Part II ^a	Randomisation	Week 2	Week 4	On treatment	Treatment discontinuation ^b	28 day Follow up ^c	Follow-up until disease recurrence ^d	Follow up for survival	Protocol Section

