5.1 Efficacy assessments

5.1.1 Disease-free survival

Disease-free survival is the primary endpoint in this study and is defined as the time from the date of randomisation until the date of disease recurrence or death from any cause in the absence of disease recurrence. Disease recurrence is defined as evidence of disease recurrence on CT or MRI scan and/or pathological disease on biopsy by investigational site assessment.

The imaging modalities used for radiological assessments will be CT scans of the chest and abdomen (including liver and adrenal glands) with contrast. In the rare case where a patient is intolerant of the contrast medium the preferred imaging would be CT chest without contrast and MRI abdomen with contrast; however a non-contrast abdominal CT will also be accepted. The methods used at baseline (CT or MRI) must be used at each subsequent follow-up assessments. A pre-surgical MRI or contrast CT scan of the brain is considered standard of

care and must be done prior to surgery. Patients in whom this was not done prior to surgery may still be enrolled providing that appropriate imaging is performed prior to randomisation. Any other sites where disease is suspected at baseline must also be imaged to confirm absence of disease prior to randomisation into the study. The baseline assessments should be performed within 28 days prior to study drug initiation. Subsequent assessments are to be performed at 12 week, 24 week and then every 24 weeks until 5 years (264 weeks), and then yearly thereafter relative randomisation, until disease recurrence is recorded. If a patient discontinues treatment prior to disease recurrence or receives other anti-cancer treatment, patient should continue to be imaged in accordance with this schedule until disease recurrence is noted. It is important to follow the assessment schedule as closely as possible. If scans are performed outside of the scheduled visit (\pm 7 days window interval) and the patient has not recurred, every attempt should be made to perform the subsequent scans at their scheduled time points. Any other sites at which a new disease is suspected should also be appropriately imaged during the study.

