8.2 Sample size estimate

Approximately 700 patients will be randomised in a 1:1 ratio (AZD9291:Placebo) to this study. The primary endpoint of the study is DFS based on investigator assessment and will be assessed firstly in the stage II-IIIA population and then the overall population.

The primary analysis of DFS is planned to occur when approximately 247 disease recurrence events have been observed in approximately 490 patients who are in Stage IIa-IIIa (i.e., non-IB). If the true DFS hazard ratio (HR) for the comparison of AZD9291 versus placebo in this patient population is 0.70, 247 disease recurrence events will provide 80% power to demonstrate a statistically significant difference in DFS at a 5% 2-sided significance level (this could translate to an improvement in median DFS from 40 months to 57 months, assuming DFS is exponentially distributed). The minimum DFS HR that would be statistically significant ($p < 0.05$, 2 sided) is 0.78.

If the true DFS HR for the comparison of AZD9291 versus placebo in the overall population is 0.70, 317 disease recurrence events will provide ~90% power to demonstrate a statistically significant difference (this could translate to an improvement in median DFS from 46 months to 66 months, assuming DFS is exponentially distributed).

At the time of the primary analysis (when approximately 247 DFS have been observed), it is anticipated that approximately 195 OS events (28% maturity) will have occurred (assuming a median OS of 96 months for the placebo arm). If the true OS HR for the comparison of AZD9291 versus placebo is 0.66, 195 death events provides approximately 80% power to

demonstrate a statistically significant difference. With 195 death events and assuming a true OS HR of 0.85 there is approximately 90% chance of observing a HR < 1.02.

Assuming 28 months non-linear recruitment, the data cut-off for the primary analysis is estimated to occur approximately 68-70 months after first patient randomised.

It is estimated that 3200 patients will be screened in order to randomise 700 patients.

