Appendix A
Study and Site Start and Closure

The study start date is the date on which the clinical study will be open for recruitment of participants.

The first act of recruitment is the 26 Aug 2015 and will be the study start date.

The sponsor designee reserves the right to close the study site or terminate the study at any time for any reason at the sole discretion of the sponsor. Study sites will be closed upon study completion. A study site is considered closed when all required documents and study supplies have been collected and a study-site closure visit has been performed.

The investigator may initiate study-site closure at any time, provided there is reasonable cause and sufficient notice is given in advance of the intended termination.

Reasons for the early closure of a study site by the sponsor or investigator may include but are not limited to:

- Failure of the investigator to comply with the protocol, the requirements of the IRB/IEC or local health authorities, the sponsor's procedures, or GCP guidelines
- Inadequate recruitment of participants by the investigator
- Discontinuation of further study intervention development

If the study is prematurely terminated or suspended, the sponsor shall promptly inform the investigators, the IECs/IRBs, the regulatory authorities, and any contract research organization(s) used in the study of the reason for termination or suspension, as specified by the applicable regulatory requirements. The investigator shall promptly inform the participant and should assure appropriate participant therapy and/or follow-up.

Participants from terminated sites will have the opportunity to be transferred to another site to continue the study.

Clinical Study Protocol Appendix B
Drug Substance AZD9291
Study Code D5164C00001
Edition Number 1.0
Date 04 June 2015

Clinical Study Protocol Appendix B

Drug Substance	AZD9291
Study Code	D5164C00001
Edition Number	1.0
Date	04 June 2015

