Following complete resection and prior to treatment initiation, all patients will be required to have a baseline computer tomography (CT) scan (chest and abdomen including liver and adrenal glands) within 28 days of study treatment initiation to confirm that disease is not present. Patients will continue on randomised treatment until recurrence of disease, treatment discontinuation criterion is met, or treatment is completed. The treatment duration period is three years. Patients being on study treatment at the time of DFS primary analysis may continue treatment until discontinuation criterion is met or three years treatment is completed. The study database will be locked at this point. A further analysis will be performed if there are significantly less than 70 DFS events in the IB population at the time of the primary analysis. If more mature data on Overall Survival is required, then it may be analysed at a later timepoint. Once the study is closed serious adverse events (SAEs) will only be reported as per Section 6.4 of the protocol.

Patients will undergo safety assessments at baseline, two weeks, four weeks, 12 weeks and every 12 weeks until treatment is completed or discontinued. All study patients must have a 28 day follow up visit after treatment is stopped.

Patients will undergo regular radiological assessments for disease recurrence at 12 weeks, 24 weeks and then every 24 weeks until five years, then yearly thereafter. DFS shall be measured from the day of randomisation until date of recurrence or death (by any cause) in the absence of recurrence by investigational site assessment.

Patients who discontinue treatment prior to disease recurrence will continue to be followed for DFS according to study plan. Following disease recurrence, patients will undergo radiological imaging for subsequent progression in accordance with local clinical practice and will be

[figure not shown]
followed for survival every six months until five years post randomisation, then yearly thereafter. Follow up will continue until the study is closed.

At disease recurrence, patients will be restaged according to the 7th edition of AJCC Cancer Staging Manual, 2010, and all sites of NSCLC relapse will be recorded. Treatments received by the patient after relapse will be determined by the physician. Post recurrence cancer treatments and procedures will be recorded.

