3.2. Efficacy Assessments

3.2.1. Disease Free Survival

DFS is defined as the time (in days) from the date of randomisation until the date of disease recurrence or death (by any cause in the absence of recurrence) regardless of whether the patient withdraws from randomised therapy or receives another anti-cancer therapy prior to recurrence (i.e. date of DFS event or censoring – date of randomisation + 1).

Patients who are disease-free and alive at the time of analysis will be censored at the date of their last assessment for disease recurrence. However, if the patient recurs or dies immediately after two or more consecutive missed visits, the patient will be censored at the time of the latest evaluable assessment for disease recurrence prior to the two missed visits. Given the scheduled visit assessment scheme (i.e. twelve-weekly for the first 24 weeks and then twenty-four-weekly thereafter) the definition of 2 missed visits will change. If the previous assessment is less than study day 78 (i.e. week 11) then two missing visits will equate to 25 weeks since the previous assessment, allowing for late visit (i.e. 2×12 weeks + 1 week for a late assessment = 25 weeks). If the two missed visits occur over the period when the scheduled frequency of assessments changes from twelve-weekly to twenty-four-weekly this will equate to 38 weeks (i.e. take the average 12 and 24 weeks which gives 18 weeks and then 2×18 weeks + 1 week of an early assessment + 1 week for a late assessment = 38 weeks). The time period for the previous assessment will be from study days 78 to 161 (i.e. week 11 up to week 23). If the previous assessment is from week 23 (day 162) onwards (when the scheduling

changes to twenty-four weekly assessments), two missing visits will equate to 50 weeks (i.e. 2 x 24 weeks + 1 week for an early assessment + 1 week for a late assessment = 50 weeks).

If the patient has no evaluable visits or does not have baseline data (chest, abdomen & brain scans), they will be censored at Day 1 unless they die within two visits of baseline (24 weeks plus 1 week allowing for a late assessment within the visit window) in which case the event will be used.

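### The SAP's 50-week limit for two missed scans ignores the yearly scans after week 264; a minor error that reaches only later, exploratory DFS analyses

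*SAP*

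**What the plan says.** SAP section 3.2.1 censors a patient at the last evaluable assessment if recurrence or death comes directly after at least two scheduled visits missed in succession. It then turns this into elapsed time. It describes the schedule as "twelve-weekly for the first 24 weeks and then twenty-four-weekly thereafter" and gives three limits by date of previous assessment:

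- before day 78: 25 weeks;
- days 78 to 161: 38 weeks;
- from day 162, with no upper bound: "changes to twenty-four weekly assessments), two missing visits will equate to 50 weeks".

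The schedule itself is different after five years. SAP section 1.2 has scans "every 24 weeks until five years, then yearly thereafter". Protocol section 1.6 has them "at 12 weeks, 24 weeks and then every 24 weeks until 5 years (264 weeks), then yearly thereafter". Protocol section 5.1.1 agrees ("then every 24 weeks until 5 years (264 weeks), and then yearly thereafter relative randomisation"), as does Table 1 in protocol section 4 ("every 24 weeks relative to randomisation (± 7 days) until 5 years, then yearly until disease recurrence").

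SAP section 7 replaces only the text on alpha allocation, so section 3.2.1 still governs the derivation of DFS. Neither document gives the week of the first yearly scan.

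**The concern.** The SAP accepts that the meaning of two missed visits changes with the scan interval and provides a step for the move from 12 to 24 weeks. It provides none for the move from 24 weeks to a year. A programmer given numeric limits and day boundaries will code them, and the code would then censor three kinds of event that the governing sentence does not intend to censor:

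- (a) a recurrence found at an on-time yearly scan, with nothing missed;
- (b) an event after a single missed scan, for example week 264 alone;
- (c) a death more than 50 weeks after the last scan when fewer than two scheduled scans were missed.

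Removing true late events lifts the tail of the DFS curve. That is where SAP section 4.3.7.2 looks for a plateau and, if one appears, fits a cure rate model.

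**Working it through.** **The plan's own limits.** The method is the sum of two scan intervals plus the visit windows: 2 x 12 + 1 = 25; 2 x (12 + 24)/2 + 2 = 38; 2 x 24 + 2 = 50 weeks. The day boundaries are 11 x 7 + 1 = 78 and 23 x 7 + 1 = 162. All are reproduced.

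**Gaps after week 240, each scan within +/- 7 days.** Three readings of the first yearly scan are possible: week 316 (264 + 52), week 313 (six calendar years) or week 312 (6 x 52).

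| Pattern | Week 316 | Week 313 | Week 312 |
|---|---|---|---|
| Week 264 to first yearly scan, on time | 50-54 | 47-51 | 46-50 |
| First to second yearly scan, on time | 50-54 | 50-54 | 50-54 |
| Week 240 to first yearly scan, only week 264 missed | 74-78 | 71-75 | 70-74 |

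Case (a) therefore starts at the first yearly scan if that is week 316, marginally so if week 313, and only at the second if week 312. Case (b) arises under every reading.

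**Which analyses are reached.** The protocol (Appendix A) states: "The first act of recruitment is the 26 Aug 2015 and will be the study start date". From then to the 17 January 2020 cut-off (protocol section 1.4) is 1605 days, and 1605/7 = 229.3 weeks, short of 264. The originally planned cut-off ("Assuming 28 months non-linear recruitment, the data cut-off for the primary analysis is estimated to occur approximately 68-70 months after first patient randomised") is weeks 296-304, before any yearly scan. The earliest week-316 scan falls at 316 x 7/30.4375 = month 72.7. Q1 2022, the expected date in SAP Table 6, is weeks 331-344 (months 76.2-79.1). The 60-month rate is read at 1826.25/7 = week 260.9.

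**Size of case (a), by simulation.** Inputs from the documents: 490 stage II-IIIA patients, exponential DFS, medians 40 and 57 months, 28-month accrual. Assumptions: every scan attended, recurrences found at scheduled scans, uniform +/- 7-day jitter, and accrual either linear or back-loaded (quadratic, since the plan calls it non-linear). A 44-month accrual is also tried (Q2 2029 less about 10 years). Events lost on the week-316 reading:

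| Analysis | 28-month accrual | 44-month accrual |
|---|---|---|
| At the 247th event | 0-0.1 | up to about 2 |
| Q1 2022, back-loaded | 0.45 of 267 to 1.77 of 276 | 0.21 of 229 to 0.78 of 240 |
| Q1 2022, linear | 3.9 of 277 to 7.4 of 287 | 2.5 of 253 to 4.6 of 260 |

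By month 91 the loss is about 6-27 events across these accrual patterns. At Q1 2022 the week-313 reading gives 0.04-0.24 (back-loaded) or 0.3-1.0 (linear), and week 312 gives none. If half of recurrences are found between scans, the week-316 figures at Q1 2022 fall to 0.1-0.9 and 1.3-3.8. Cases (b) and (c) are not in these counts.

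**Hazard ratio.** With a constant ratio near 0.70 the largest change at Q1 2022 is 0.7039 to 0.7024. If the effect is assumed to wane (0.2 to week 156, then 1.0 or 1.5; linear accrual), the change at month 78 is 0.011-0.018, for example 0.450 to 0.438. At month 91 it is up to 0.046 (0.619 to 0.573). In these waning runs the error favours AZD9291.

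**The case against.** The best defence has four parts.

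- *The governing sentence is right.* It speaks of missed visits, so a careful programmer could override the number. That makes this an incomplete operational definition rather than a wrong principle, but code follows stated limits and days.
- *The main mechanism depends on an unstated week.* This stands. Protocol section 5.2.3 equates the first year of ECG collection with week 48. If every yearly interval were 48 weeks, on-time gaps would be 46-50 weeks and case (a) would vanish. Elsewhere, though, three years is 156 weeks, that is 52 per year, and case (b) remains either way.
- *The exploratory DFS analysis is event-driven.* This also stands. With 28-month accrual, 247 events arrive on average at about month 66 (linear) or 70 (back-loaded), before the first possible week-316 scan. The figure of 7.4 of 287 belongs to a calendar cut-off 40 events past the trigger.
- *The attrition-bias analysis in SAP section 4.3.7.1(c) puts the events back.* It does restore the actual DFS times. In the same run it also censors patients at subsequent therapy, so it neither isolates this error nor corrects the main curve and the plateau assessment.

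A reader might infer that the reported DFS benefit, or its significance, is inflated. The documents do not support that: nobody could have reached week 264 by the tested cut-off, and SAP section 7 makes all later DFS analyses exploratory.

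**Conclusion.** Section 3.2.1 is wrong as written for scans after week 264 and contradicts the SAP's own design section. The consequence is minor. The effect on the tested DFS result is zero. It would also be too strong to say that the five-year DFS rate is biased. With full attendance, the wrongly applied censoring falls at about week 264 or later, after week 260.9. If week 264 is missed, censoring moves back to week 240, and the risk set just before the landmark changes trivially.

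At the planned 247-event analysis the loss is negligible under the documents' 28-month accrual and about two events at most under 44 months. It becomes noticeable only if DFS follow-up runs on. That is possible for stage IB, which had 196 - 156 = 40 events at IDMC7 (SAP section 7) against the 63 below which follow-up continues (protocol section 8.7). No stage IB figure was computed; the counts are for stage II-IIIA. All sizes rest on the stated assumptions about accrual, attendance and the first yearly scan. The negligible change in hazard ratio holds for a constant ratio near 0.70. The contradiction in the text needs no assumption.

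**What to change.** Correct the schedule wording in SAP section 3.2.1, state the week of the first yearly scan, and add three limits by the SAP's own method. F is the interval in weeks from week 264 to the first yearly scan.

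| Previous assessment | Limit (weeks) | F = 52 | F = 49 | F = 48 |
|---|---|---|---|---|
| Days 1674-1841 | 24 + F + 2 | 78 | 75 | 74 |
| Day 1842 to day 2205, 2184 or 2177 | F + 52 + 2 | 106 | 103 | 102 |
| Day 2206, 2185 or 2178 onwards | 2 x 52 + 2 | 106 | 106 | 106 |

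The boundaries lie one week before the scheduled scans: 239 x 7 + 1 = 1674, 263 x 7 + 1 = 1842, and 315, 312 or 311 x 7 + 1 = 2206, 2185 or 2178. If all yearly intervals are meant to be 48 weeks, the last two limits become 2 x 48 + 2 = 98.

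With these limits no on-time event is lost. Gaps with one missed scan stay within the limit (for F = 52, 74-78 against 78 and 102-106 against 106), and gaps with two missed scans exceed it. Apply them to every DFS analysis that includes scans after week 264. The cost is about three sentences and a small programming change, with no new data and no change to the tested result.
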